6.6.3 Days 3 and 24 – Inpatient CRU

- Obtain PK blood sample 48 hours (± 30 min) after dosing.
- Assess reactogenicity at SC injection site at 48 h (± 30 min) post dose (see [Section 7.1.4](#) and MOP for this study).
- Assess AEs.

- Review and record any concomitant medications and non-pharmacologic treatments/procedures since admission to the CRU.

6.6.4 Days 4 and 25 – Inpatient CRU

- Obtain resting vital signs 72 hours (± 30 min) after being at rest for at least 5 minutes.
- Perform targeted PE.
- Assess reactogenicity at SC injection site at 72 h (± 30 min) post dose (see [Section 7.1.4](#) and MOP for this study).
- Assess AEs.

6.6.5 Days 5 and 26 – Inpatient CRU

- Obtain PK blood sample 96 hours (± 30 min) after dosing.
- Assess reactogenicity at SC injection site at 96 h (± 30 min) post dose (see [Section 7.1.4](#) and MOP for this study).
- Assess AEs.
- Review and record any concomitant medications and non-pharmacologic treatments/procedures since admission to the CRU.

6.6.6 Days 6 and 27 – Inpatient CRU

- Assess reactogenicity at SC injection site at 120 h (± 30 min) post dose (see [Section 7.1.4](#) and MOP for this study).
- Assess AEs.

6.6.7 Days 7 and 28 – Inpatient CRU

- Obtain resting vital signs 144 hours (± 30 min) after being at rest for at least 5 minutes.
- Perform targeted PE.

- Obtain blood for hematology/coagulation/chemistry and urine for urinalysis.
- Obtain PK blood sample 144 hours (± 30 min) after dosing.
- Assess reactogenicity at SC injection site at 144 h (± 30 min) post dose (see [Section 7.1.4](#) and MOP for this study).
- Assess AEs.
- Review and record any concomitant medications and non-pharmacologic treatments/procedures since admission to the CRU.
- Counsel on contraceptive use and provide post-discharge instructions (dietary and medication/nonmedication, vaccine and blood/blood product/sperm donation restrictions),
- Train on proper completion of Memory Aid (Day 7), refresher (Day 28).
- Subject discharge from CRU after all procedures completed.

6.6.8 Days 14 (± 1 Day) and 35 (± 1 Day) – Follow-Up - Outpatient

- Obtain vital signs after resting in a supine or semi-supine position for at least 5 minutes.
- Perform targeted PE.
- Obtain PK blood sample.
- Assess reactogenicity at SC injection site (see [Section 7.1.4](#) and MOP for this study).
- Assess AEs.
- Review and record any concomitant medications and non-pharmacologic treatments/procedures since discharge from the CRU.
- Review Memory Aid.
- Reminder of contraceptive use and post-discharge instructions (dietary and medication/nonmedication, vaccine and blood/blood product/sperm donation restrictions).

6.6.9 Day 52 (± 1 Day) – Follow-Up – Final Study Visit

- Obtain vital signs after resting in a supine or semi-supine position for at least 5 minutes.
- 12-lead ECG after at least 5 minutes in the supine position (triplicate readings, at least 1 minute apart within a 15-minute period).
- Perform targeted PE.
- Obtain weight, calculate BMI.
- Obtain blood for hematology/coagulation/chemistry and urine for urinalysis.
- Perform serum pregnancy test (females only).
- Obtain PK blood sample.
- Assess AEs.
- Review and record any concomitant medications and non-pharmacologic treatments/procedures since Day 35.
- Review Memory Aid.
- Review post-study instructions (contraceptive use, pregnancy reporting).

6.6.10 Early Termination (ET) Visit (if needed)

The CRU will make every effort to perform all assessments listed for the last scheduled FU visit if a subject is terminated prematurely from this trial. All information collected will be documented in eCRFs or study records.

6.7 Unscheduled Study Visits

Subjects will return to the CRU at the direction of the Site PI for FU and data from unscheduled visits or procedures (if any) and will be captured and presented in data listings. These data will be clearly identified as unscheduled observations. Safety assessments, including updated history, AEs, PE, and any other trial procedures deemed necessary by the PI, will be obtained.

Subjects returning to the CRU for unscheduled visit(s) may undergo procedures, including but not limited to, the following, which are listed in the Schedule of Study Procedures and Evaluations ([Appendix A](#)) and detailed in Clinical Evaluations ([Section 7](#)):

- Review and record any concomitant medications and non-pharmacologic treatments/procedures since last visit,
- Obtain a 12-lead ECG after at least 5 minutes in the supine position (triplicate readings, at least 1 minute apart within a 15-minute period),
- Obtain blood for hematology/coagulation/chemistry and urine for urinalysis,
- Perform targeted PE including resting vital signs (heart rate, blood pressure, oral temperature, and respiration rate, taken after resting for at least 5 minutes). If abnormal, these measurements may be repeated once,
- Review Memory Aid,
- Assess AEs.

6.8 Protocol Deviations

A protocol deviation is any noncompliance with this protocol, GCP, or protocol-specific MOP requirements. The noncompliance may be either on the part of the subject, the Site PI, or the site personnel. As a result of deviations, corrective actions will be developed by the site and implemented promptly.

These practices are consistent with ICH E6:

- 4.5 Compliance with Protocol, Sections 4.5.1, 4.5.2, and 4.5.3
- 5.1 Quality Assurance (QA) and Quality Control (QC), Section 5.1.1
- 5.20 Noncompliance, Sections 5.20.1, and 5.20.2.

It is the responsibility of the Site PI and personnel to use continuous vigilance to identify and report deviations within 5 working days of identification of the protocol deviation, or within 5 working days of the scheduled protocol-required activity. All deviations must be promptly reported to DMID per the Statistical and Data Coordinating Center (SDCC) protocol deviation reporting procedures.

All protocol deviations, as defined above, must be addressed in subject data collection forms (DCFs). Protocol deviations must be sent to the local IRB/IEC per their guidelines. The Site PI and personnel are responsible for knowing and adhering to their IRB requirements.

7 DESCRIPTION OF CLINICAL AND LABORATORY EVALUATIONS

7.1 Clinical Evaluations

7.1.1 Medical History

Medical history will be obtained by direct interview. Subjects will be queried regarding a history of significant medical disorders of the head, eyes, ears, nose, throat, mouth, cardiovascular system, lungs, gastrointestinal tract, liver, pancreas, kidney, urologic, nervous system, blood, lymph glands, endocrine system, musculoskeletal system, skin, and genital/reproductive tract. A history of any allergies, cancer, immunodeficiency, psychiatric illness, substance abuse, and autoimmune disease will be solicited. The medical history will include current and past medical diagnoses, hospitalizations and major surgical procedures. Demographic information (date of birth, gender, race, ethnicity) will be obtained as part of the medical history assessment. The medical history will be obtained at screening and updated upon admission to the CRU on Day -1.

7.1.2 Height, Weight, Body Mass Index (BMI)

All subjects will have height measured (at Screening only) and be weighed following the CRU's standard operating procedures at Screening, Day -1 and at the final study visit. BMI is calculated as: (weight in kg divided by height in m, squared). Subjects who no longer meet inclusion criteria due to changes in weight or BMI after dosing remain eligible and will not be removed from the study.

7.1.3 Physical Examinations

A complete PE at Screening will evaluate vital signs (taken after resting for at least 5 minutes); general appearance; head, eyes, ears, nose, and throat; neck; chest and lungs; cardiovascular system, abdomen, musculoskeletal system, lymph nodes, extremities/skin, and neurological system.

A targeted PE will evaluate resting vital signs, skin, and suspected organ systems described in any solicited or unsolicited AEs, at times specified in [Appendix A](#).

7.1.4 Local Reactogenicity Symptoms

Reactogenicity assessments will include an assessment of AEs occurring after dose administration on Day 1 through Day 30 of Part 1 (SAD), Day 30 of Part 2 (MAD) or Day 35 of

Part 3 (BA), which includes an assessment of SC injection site reactions (see Additional Characterization of Reactogenicity at Injection Sites, below). Pre-administration (baseline) injection site skin assessments will be performed prior to each study injection to establish baseline, then the study injection will be given.

The study SC injection site(s) will be examined pre-dose and at 1 and 4 h (\pm 10 minutes), 24, 48, 72, 96, 120, 144 h (\pm 30 minutes) post-administration in all cohorts (SAD/MAD/BA). Additional injection site examinations will occur on Day 14 of Part 1 (SAD), Day 30 of Part 2 (MAD), and Days 14 and 35 of Part 3 (BA), and any AE/SAEs will be recorded on the appropriate data collection form.

Additional Characterization of Reactogenicity at Injection Sites

Lesions at the injection site will be characterized by the study site staff as follows:

1. Ecchymosis: non-raised skin discoloration caused by the escape of blood into the tissues from ruptured blood vessels
2. Erythema: localized redness
3. Induration: (hardness)/swelling
4. Nodule: solid or cystic raised bump in the skin
5. Ulcer: an open lesion on the surface of the skin caused by superficial loss of tissue. NOTE: Ulcers at the injection site, regardless of size or severity, are of special interest and must be measured as well as photographed*, according to the MOP for this study. Please see [Section 8.1.3](#) for reporting details and [Section 8.7](#) for halting rules.
6. Healed**: previously observed lesion that has dried up without any persistent induration or ulcer.
7. Scar**: replacement of normal skin with fibrous tissue

*All SC site reactions will be photographed at each visit, scheduled and unscheduled until resolution.

**Recorded, but not graded.

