3.1.1.3 Part 3 (BA)

Part 3 of this study may be run in parallel with Cohort 7 of the Part 2 (MAD) portion of this study, upon completion of safety data review for all Cohorts 1-6 of Part 1 (SAD). In the unblinded Part 3 cross-over portion of this trial, 10 subjects will be randomized to one of two sequences of 5 subjects each to receive a SC→IV or IV→SC sequence of study drug administration. In sequence 1 (SC→IV), rezafungin (100 mg or MTD in Part 1) administered by SC injection on Day 1 followed by rezafungin (100 mg or MTD in Part 1) administered by IV infusion over 60 minutes on Day 22; or in Sequence 2 (IV→SC), rezafungin (100 mg or the maximum tolerated dose in Part 1) administered by IV infusion over 60 minutes on Day 1 followed by rezafungin (100 mg or the maximum tolerated dose in Part 1) administered by SC injection on Day 22. Maximum tolerated dose (MTD) is defined as the highest dose level with no withdrawals by subject or investigator due to AEs related to study product for Part 1 (SAD) Cohorts 1-6. A schematic of the BA study design is shown in [Table 3](#).

Table 3: Design for SC Dosing in Absolute BA Cohort (Study Part 3)

Sequence		Day 1 (Period 1) Dose/Volume/Route	Day 22 (Period 2) Dose/Volume/Route	Number of Subjects*
1 (SC → IV)		100 mg x 1 mL SC injection	100 mg 250 mL IV infusion	5
2 (IV → SC)		100 mg 250 mL IV infusion	100 mg 1 mL SC injection	5
Total Number of Subjects				10

*Part 3 may be run following the cohort dosed at the same dose level (100 mg or MTD) in Part 1 (SAD).

The BA of the SC dose compared to the IV dose will be determined as the ratio of the rezafungin area under the plasma concentration versus time curve (AUC) values from each administration.

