6.4.10 Day 30 (± 1 Day) – Follow-Up – Final Study Visit

- Obtain resting vital signs after being at rest for at least 5 minutes.
- 12-lead ECG after at least 5 minutes in the supine position (triplicate readings, at least 1 minute apart within a 15-minute period).
- Perform targeted PE.
- Obtain weight, calculate BMI.
- Obtain blood for hematology/coagulation/chemistry and urine for urinalysis.
- Perform serum pregnancy test (females of childbearing potential only).
- Obtain PK blood sample. No PK blood samples collected in Cohort 1.
- Assess reactogenicity at SC injection site(s) (see [Section 7.1.3](#) and MOP for this study).
- Assess AEs.
- Review Memory Aid.
- Review and record any concomitant medications and non-pharmacologic treatments/procedures since admission to the CRU.
- Review post-study instructions (contraceptive use, pregnancy reporting).

6.5 Part 2 (Cohorts 7 through 10)**6.5.1 Days 1, 8, and 15 – Inpatient CRU**

Study drug or placebo will be administered via SC injection in the morning on Days 1, 8, and 15. Subjects will be inpatients in the CRU and will undergo the following procedures, which are listed in the Schedule of Study Procedures and Evaluations ([Appendix A](#)) and detailed in Clinical Evaluations ([Section 7](#)):

- Randomize the subject (Day 1 only).
- Review inclusion criteria numbers 2-7 and 10-11, and exclusion criteria numbers 2-4 and 8-18 (from [Section 5.1.2](#)) to ensure the subject remains eligible for dosing (Days 8 and 15 only).
- Obtain resting vital signs before study drug dosing (within 60 minutes of study drug dosing for Day 1). This is to be documented as the Baseline prior to dosing on Day 1.
- Perform targeted PE.
- Obtain a 12-lead ECG before study drug dosing (Day 1 only) after at least 5 minutes in the supine position (triplicate readings, at least 1 minute apart within a 15-minute period) and within 60 minutes before study drug dosing.
- Baseline (Day 1) and pre-dose (Days 8 and 15) skin assessment at SC injection site area(s) prior to study drug dosing (see [Section 7.1.3](#) and MOP for this study).
- Administer study drug via SC injection in the abdomen at a slow, steady pace.
- Obtain vital signs at 15 minutes (± 5 min), 1 hour (± 10 min), and 2 hours (± 10 min) after dosing, after resting in a supine or semi-supine position for at least 5 minutes.

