6.6 Part 3 (Cohort 11)**6.6.1 Days 1 and 22 – Inpatient CRU**

For Cohort 11, the subject will be randomized to sequence and either the study drug will be administered via SC injection in the morning on Day 1 and as an IV infusion over 60 (± 5) minutes in the morning on Day 22; or the study drug will be administered via IV infusion over 60 (± 5) minutes in the morning on Day 1 and via SC injection in the morning on Day 22. Subjects will be inpatients in the CRU and will undergo the following procedures, which are

listed in the Schedule of Study Procedures and Evaluations ([Appendix A](#)) and detailed in Clinical Evaluations ([Section 7](#)):

- Randomize the subject (Day 1 only).
- Review inclusion criteria numbers 2-7 and 10-11, and exclusion criteria numbers 2-4 and 8-18 (from [Section 5.1.2](#)) to ensure the subject remains eligible for dosing (Day 22 only).
- Obtain resting vital signs before study drug dosing (within 60 minutes of study drug dosing. This is to be documented as the Baseline prior to dosing on Day 1).
- Perform targeted PE.
- Obtain a 12-lead ECG within 60 minutes of study drug dosing, (Day 1 only), after at least 5 minutes in the supine position (triplicate readings, at least 1 minute apart within a 15-minute period).
- Baseline skin assessment at SC injection site area prior to study drug dosing: assess reactogenicity at SC injection site before study drug dosing on Day 22 (see [Section 7.1.3](#) and MOP for this study).
- Administer study drug.
- Obtain vital signs (SC): at 15 minutes (± 5 min), 1 hour (± 10 min), and 2 hours (± 10 min) after dosing, after resting in a supine or semi-supine position for at least 5 minutes.
- Obtain vital signs (IV): at 15 minutes (± 5 min), 1 hour (± 10 min), and 2 hours (± 10 min) after start of infusion, and after resting in a supine or semi-supine position for at least 5 minutes.
- Obtain PK blood samples within 60minutes before study drug dosing and at 0.5 h (± 5 min), 1 h (± 10 min), 2 h (± 10 min), 4 h (± 10 min), 6 h (± 10 min), 8 h (± 10 min), and 12 h (± 10 min) after the start of infusion or injection.
- Post dose ECG (SC) at 4 hours (± 10 minutes) after SC injection, 12-lead ECG after at least 5 minutes in the supine position (triplicate readings, at least 1 minute apart within a 15-minute period).

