	-28 to -2	-1 and 21	1	2	3	4	5	6	7	14 and 35 (± 1)	52 (± 1)		
			22	23	24	25	26	27	28				
Informed Consent Form ^a	X												
Assessment of Eligibility Criteria	X	X											
Demographics	X												
Height ^b , Weight, BMI	X	X									X		
Review of Medical History	X	X											
Hepatitis and HIV tests ^c	X												
Follicle-stimulating hormone (FSH) test ^d	X												

Procedures/Day	Screening	Baseline Check-in	Inpatient – Confined to CRU							FU	FU/ET	Unscheduled	
	-28 to -2	-1 and 21	1	2	3	4	5	6	7	14 and 35 (±1)	52 (±1)		
			22	23	24	25	26	27	28				
Pregnancy test ^e	X	X									X		
Review of Concomitant Medications	X	X	X		X		X		X	X	X	X	
Study drug randomization just prior to dosing ^f			X										
Administration of study drug ^g			X										
Vital signs ^h	X	X	X	X		X			X	X	X	X	
Physical examination ⁱ	X	X	X	X		X			X	X	X	X	
12-lead ECGs ^j	X		X								X	X	
Blood for hematology & coagulation ^k	X	X		X					X		X	X	
Blood for chemistry panel ^k	X	X		X					X		X	X	
Urine for urinalysis ^l drug screen, alcohol ^l	X	X		X					X		X	X	
Urine cotinine	X	X											
Blood for PK analysis ^m			X	X	X		X		X	X	X	X	
Reactogenicity evaluation ⁿ			X	X	X	X	X	X	X	X		X	
Assess for AEs ^o			X	X	X	X	X	X	X	X	X	X	
Counsel/reminders ^p	X								X	X	X	X	
Memory Aid ^q		X	X						X	X	X	X	

Abbreviations: AE: adverse event; BMI: body mass index; CRU: clinical research unit; ECG: electrocardiogram; FU: follow-up; HIV: human immunodeficiency virus; PK: pharmacokinetic.

- Informed consent will be obtained before initiating any trial-related assessments and procedures,
- Height at Screening only,
- Screen (serum) for hepatitis B surface antigen, hepatitis C virus antibody, and HIV antibody,
- Perform FSH (serum) test for postmenopausal (females only),
- Perform serum pregnancy tests at Screening Day -1 and Day 52 females only,
- Randomize subjects on Day 1 only,
- A single dose of study drug will be administered via SC injection/IV infusion on Days 1 and 22,

- h. Vital signs will be obtained at Screening; on Day -1; on Days 1 and 22 within 60 minutes to study drug administration and at 15 minutes (± 5 min), 1 and 2 hours (± 10 min), post-dose; and on Days 2, 4, 7, 23, 25, 28 (± 30 min) and 14 (± 1 day), 35 (± 1 day), and 52 (± 1 day),
- i. A complete PE will be performed at Screening and targeted PEs will be performed on Days -1, 1, 2, 4, 7, 14, 22, 23, 25, 28, 35, and 52. Days 14, 35, and 52 have (± 1 day) window.

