- j. ECGs will be obtained at Screening and on Day 1 within 60 minutes prior to study drug administration, and 4 hours (± 10 minutes) post-dose (SC) and 1 hour (± 10 minutes) post-dose (IV) from start of infusion for IV admin, Day 52, and Unscheduled visits
- k. Fasting (at least 8 hours) blood samples will be collected for hematology, coagulation and chemistries at Screening and on Days -1, 2, 7, 23, 28, and 52 (± 1 day). Hematology tests consist of CBC with differential; coagulation tests consist of PT/PTT/INR; Chemistries panel includes albumin, glucose, blood urea nitrogen or urea, potassium, calcium, sodium, chloride, total protein, creatinine, CO₂, CK, phosphorus, alkaline phosphatase, AST, ALT, total bilirubin, direct bilirubin,
- l. Urine will be collected for urinalysis, urine drug screen and urine alcohol at Screening, and on Day -1. Urine will be collected for urinalysis on Days 2, 7, 23, 28, and 52 (± 1 day),
- m. Blood for PK analysis (plasma) will be drawn pre-dose within 60 minutes before study drug dosing and at 0.5(± 5 min), 1, 2, 4, 6, 8, and 12 hours (± 10 min) on Days 1 and 22; 24 hours (± 30 min), on Days 2 and 23; 48 hours(± 30 min) on Days 3 and 24; 96 hours (± 30 min), on Days 5 and 26; and 144 hours (± 30 min) on Days 7 and 28 after dosing; and on Days 14 and 35 (± 1 day) and 52 (± 1 day),
- n. Injection site assessment pre-dose and at 1 and 4 (± 10 min), 24, 48, 72, 96, 120, and 144 h (± 30 min) post-dose, Day 14 (± 1 day), and Day 35 (± 1 day). Unscheduled visits are not timed.
- o. Subjects are to be assessed for AEs occurring from the time of the first dose of study drug through Day 52 (± 1 day),
- p. Counsel/reminder on contraceptive use and post-discharge instructions (dietary and medication/nonmedication, vaccine and blood/blood product/sperm donation restrictions); as described in **Section 5.1**.
- q. Memory Aid issued on Day 1, training on Day 7 (refresher on Day 28), reviewed on Days 21, 14, 35, 52 and at Unscheduled visits.

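### Minor, cheap to fix: Part 3's Day 52 final and early-termination visit schedules no injection-site assessment, so the last scheduled check in IV→SC is 13 days after the SC dose

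*Protocol*

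**What the plan says.** **Part 3 dosing.** Under Section 3.1.1.3, ten subjects are randomized five to each sequence. SC→IV subjects have the SC injection on Day 1. IV→SC subjects have it "administered by SC injection on Day 22".

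**Part 3 site checks.** The site is examined pre-dose and eight times from 1 to 144 hours after SC dosing. Section 7.1.4 then adds "Days 14 and 35 of Part 3 (BA"). Section 6.6.1 also has staff "assess reactogenicity at SC injection site before study drug dosing on Day 22", which in SC→IV is a further check of the injected site.

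**Part 3 final visit.** The Day 52 list in Section 6.6.9 includes vital signs, ECG, targeted examination, laboratory tests, PK, adverse events, Memory Aid review, and medications and "non-pharmacologic treatments/procedures since Day 35". It has no reactogenicity item. In Table 13 the "Reactogenicity evaluation" row is blank in the Day 52 FU/ET column. Footnote n, which begins "Injection site assessment pre-dose and at 1 and 4", ends at Day 35. Section 6.6.10 gives early terminators the assessments of the last scheduled follow-up visit, so they inherit the omission.

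**Parts 1 and 2.** The Part 1 final visit (Day 30, Section 6.4.10) carries the instruction "Assess reactogenicity at SC injection site(s"). The Part 2 final visit (Day 45, Section 6.5.9) carries the same item. Footnote n of Tables 11 and 12 and the endpoints in Section 3.3.1 agree with Days 30 and 45.

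**The concern.** Local toxicity is the main risk of the SC route in this trial. Ulceration of any grade at an injection site is an event of special interest (Section 8.1.3) and stops dosing pending SMC review (Section 8.7.1). Section 10.5.3 plans to summarize ulcers by size and resolution. Parts 1 and 2 schedule a site check about a month after the last SC dose. Half of Part 3 has its last one at about two weeks, although those subjects return on Day 52 in any case.

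At stake is systematic information from day 13 to about day 30 after SC dosing: whether the site is clear, whether an earlier reaction has resolved, and whether anything new has appeared. Without a scheduled item, a missing Day 52 entry cannot be told apart from a clear site. Part 3's listed endpoint is bioavailability (Section 3.3.2), so this is safety monitoring and does not touch the estimate of F.

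**Working it through.** The plan states no figure for length of site follow-up after SC dosing, so there is none to reproduce. The check is day arithmetic: last scheduled site assessment minus day of the last SC dose, with the ±1 day window on outpatient visits.

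| Group | Last SC dose | Last scheduled site check | Days after SC (window) |
|---|---|---|---|
| Part 1 | Day 1 | Day 30 | 30 − 1 = 29 (28–30) |
| Part 2 | Day 15 | Day 45 | 45 − 15 = 30 (29–31) |
| Part 3, SC→IV | Day 1 | Day 35 | 35 − 1 = 34 (33–35) |
| Part 3, IV→SC | Day 22 | Day 35 | 35 − 22 = 13 (12–14) |

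The two Part 3 sequences have the same post-dose schedule up to day 13:

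- Checks at 1, 4, 24, 48, 72, 96, 120 and 144 h: 8.
- One outpatient check: 14 − 1 = 13 d in SC→IV, or 35 − 22 = 13 d in IV→SC. Total 9 in each sequence.

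After day 13:

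- SC→IV has at least two more: 22 − 1 = 21 d (before the Day 22 infusion) and 34 d.
- IV→SC has none.

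With the assessment added at Day 52:

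- IV→SC: 52 − 22 = 30 d (29–31), in line with Parts 1 and 2.
- SC→IV: 52 − 1 = 51 d (50–52).

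The monkey data in Section 3.1.2 bear on whether the extra interval matters:

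- **Onset.** Most low-dose lesions appeared on Days 11 to 14 and were linked to the Day 9 injection: 11 − 9 = 2 to 14 − 9 = 5 days. One appeared on Day 12 at the Day 3 site: 12 − 3 = 9 days. All fall inside the 13 days already covered.
- **Resolution.** Low- and mid-dose findings had reversed after 4 weeks of recovery. A check at 30 days is on that timescale and one at 13 days is not. The animals were dosed repeatedly, so this is only a rough guide to a single human injection.

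**The case against.** The strongest reply is that the plan already catches late reactions. At Day 52 there is a targeted examination, which covers skin (Section 7.1.3), along with an adverse-event assessment and Memory Aid review. Section 8.1.1 collects solicited local events to the final visit and requires all AEs to be graded, using Appendix B, which contains the local-reaction scales. Section 8.2.1 has skin reactions at the site measured and photographed, and Section 7.1.4 continues photographs until resolution. All of this stands. A reader might infer that late reactions in IV→SC would be missed or left ungraded. The documents do not support that.

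Second, Part 3 uses 100 mg or the Part 1 MTD and starts only after FDA review of all Part 1 safety data. From Cohort 2 upward, six active subjects at the chosen dose would already have site checks to 29 days. This also stands, and makes a lighter late schedule defensible.

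Third, Section 7.1.4 taken alone ends Part 2 at Day 30, or 30 − 15 = 15 days after the last dose, much like Part 3's 13. That is true of that section. But Sections 3.3.1 and 6.5.9 and Table 12 all carry the Part 2 assessment to Day 45, so the contrast between parts holds.

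Two other readings go too far. SAP Table 11 has a separate row from Day 22 to the final visit, which might suggest an interval that Part 3 cannot fill. That SAP covers only Cohorts 1 and 2 and sets no Part 3 reporting interval. A reader might also infer that Day 35 would mix 13-day and 34-day observations. That would follow only if Part 3 were tabulated by study day, which no document says. Section 10.5.3 is silent on the clock for the crossover, and detail was deferred to the SAP.

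**Conclusion.** The gap is real and minor. Part 3 is the only part whose final and early-termination visit schedules no injection-site assessment. The effect on length of site follow-up falls on IV→SC, 5 of 10 planned subjects, where scheduled checks stop 29 − 13 = 16 days sooner after SC than in Part 1 and 30 − 13 = 17 days sooner than in Part 2. The loss is a recorded negative or resolution status, not detection of reactions that are seen or reported. The Part 3 sources agree with one another, so this is a design choice that can be improved, not a contradiction.

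This assumes SC dosing on Day 22 as planned, and that the MOP, which is not among the documents, adds no Day 52 site check. The SAP Preface reports that no one entered the bioavailability cohort, so no collected data are affected.

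**What to change.** Add the injection-site reactogenicity assessment to the Day 52/ET visit: one line in Section 6.6.9, Day 52 in the Part 3 wording of Section 7.1.4, a mark in the Day 52 FU/ET cell of Table 13, and Day 52 in footnote n. Have the form record a clear site or a resolved reaction as well as any graded finding. Section 6.6.10 then carries the item to early terminators without further change.

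The cost is one form entry and a few minutes per subject at a visit that already includes a skin examination. No new visit is needed.

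As an optional clarification, one sentence could say that Part 3 local reactions are indexed by days since the SC injection, extending the rule Section 10.5.3 already applies to multiple sites.
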